13.2.3. Pharmacokinetics

Pharmacokinetic (PK) data of steady state glucagon concentrations following continuous subcutaneous infusion will be analyzed descriptively.

13.2.4. Device Performance

The following endpoints related to device performance will be analyzed descriptively.

- Comparison of target vs. a weight-based estimate of dose volume delivery
- Infusion site leakage
- Occlusions
- Device failures/malfunctions

13.2.5. Safety/Tolerability

Safety/tolerability endpoints to be analyzed by treatment period will include:

- Adverse events (AEs)
- Laboratory safety variables
- Physical examination
- Body weight
- Vital signs
- Local tolerability

13.2.5.1. Adverse events:

All AEs will be coded using Medical Dictionary for Regulatory Activities (MedDRA) and summarized by system organ class and study drug. A summary table indicating the number and the percentage of exposed subjects having at least one AE will be made.

13.2.5.2. Laboratory safety assessments:

Laboratory values (biochemistry and hematology) will be flagged if outside the normal range. A listing of abnormal values will be presented in an end of text (EOT) listing. The individual values will be listed indicating values outside normal range. Laboratory assessments will be summarized for each applicable time point.

13.2.5.3. Physical examination:

Subjects with any findings in the physical examination evaluation at screening will be listed. Changes to physical examination will be recorded as AEs if the Investigator judges these as being clinically significant.

13.2.5.4. Vital signs:

Vital signs will be summarized by descriptive statistics.

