- Photograph the application site and assess for edema and erythema using the Draize scale, with particular attention to the cannula insertion site.

Period 3. Open-label Treatment

Note: For subjects not meeting the criteria for response at 24 hours, the open-label period will begin after 24 hours of blinded study drug. For subjects meeting the criteria for response at 24 hours, the open-label period will begin after 48 hours of blinded study drug.

At the start of day open-label treatment:

- Using the same procedures for loading and weighing the pump, and confirming cannula deployment as detailed for Day 0, place a new OmniPod® pump containing CSI-Glucagon™ solution (5 mg/mL concentration) and run for 4 hours.
- Basal rate should initially be set at 5 µg/kg/hr with hourly POC glucose measurements and fluid adjustments as per Period 2.
- At 4 hours, remove and the OmniPod® pump and:
 - Photograph the application site, paying particular attention to the cannula insertion site.
 - Assess site for edema and erythema using the Draize scale. Any Draize scores >0 should be followed to resolution, including a follow-up photograph.
- Determine whether, in the investigator's assessment, continued treatment is helpful for clinical care.
 - If yes, and open-label treatment will be continuing, perform "real-world" pump change-out procedure (see Section 9.3.3).
 - If no, and open label treatment is ending, remove CGM and draw blood for immunogenicity testing, plasma insulin and glucagon levels as well as CBC and CMP. Do not perform the "real-world" pump change-out procedure in this case.
- If yes, therapy may continue, including intermittently should procedures, e.g., PET scan, require temporary discontinuation, for up to a cumulative 28 days of glucagon exposure.

- A new OmniPod® pump containing CSI-Glucagon™ solution should be placed at least every 72 hours. The procedures for loading and weighing the pump and confirming successful cannula deployment should be followed each time a new pump is placed.
 - Each time a pump is replaced, determine safety of pump switch out procedures as assessed by occurrence of blood glucose < 50 mg/dL.
 - Each time a pump is removed, including at final termination of therapy, it should be weighed to the nearest whole mg, and the placement site should be photographed and assessed with Draize scales.
 - At least 2 hours prior to each planned pump change, confirm the CGM sensor is working and place another as needed.

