If this interim hypergeometric one-tailed p value is greater than 0.0124 but less than or equal to 0.05, then the study will continue and an additional 3 more subjects per study arm will be randomized. If this interim one-tailed p value exceeds 0.05 then the study will continue, and an additional 6 subjects will be randomized. The final analysis will be based on the observed treatment and placebo failure rates using all subjects with a success-failure determination. If, at the final analysis, the observed treatment failure rate is lower than placebo so that the one-tailed hypergeometric p value is less than or equal to 0.04 then treatment efficacy will be established

The actual type 1 errors are smaller than the efficacy criteria would suggest because of the small sample sizes and the use of Fisher's exact test. From Monte-Carlo simulations the overall type 1 error for this design is bounded above by 0.016 for null hypothesis treatment = placebo failure rates at any failure rate using the above criteria.

Secondary analyses will include baseline adjusted analyses of the natural logarithm of GIR to obtain confidence bounds on ratio of treatment to placebo mean GIR. Other secondary endpoints will consider the average GIR over the last 24 hours during period 2. The chance that this final rate is less than 8 mg/kg/min will be estimated and compared. Also, the cumulative glucose infusion will be combined with the total enteric feeding for the last 24 hours. The chance that this combined value is less than or equal to 8 mg/kg/min will be estimated and compared.

Pharmacokinetic (PK) data of steady state glucagon concentrations following continuous subcutaneous infusion will be analyzed descriptively.

Safety analysis: all subjects who have received at least one dose of study medication will be included. Safety data will be presented in tabular and/or graphical format and summarized descriptively. For continuous data, change from baseline will be analyzed using analysis of covariance. The proportion of study participants experiencing a particular AE will be compared by group (dose) using Fisher's Exact Test.

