5.2. Secondary Objectives

The secondary objectives are to:

1. Compare average proportional GIR reduction from baseline between CSI-Glucagon™ and placebo.
2. Compare the percentage of subjects in each group that achieve $\text{GIR} \leq 8$ mg/(kg*min) during treatment.
3. Compare the percentage of subjects in each group that achieve daily total caloric intake from carbohydrate, combining oral, tube and IV sources \leq equivalent to 8 mg/(kg*min) glucose.
4. Describe the proportion of subjects in each group that discontinue IV glucose infusion as well as the proportion of subjects that discontinue continuous naso-gastric feeds (ability of patient to fast for 3 hrs.).
5. Compare proportional time < 70 mg/dL as well as proportional time in euglycemia (≥ 70 mg/dL and < 180 mg/dL) from CGM assessments.
6. Compare device performance between the groups, including:
 - weight-based estimate of dose volume delivery
 - infusion site leakage
 - device failures/malfunctions
7. Assess safety of pump switch out procedure as assessed by occurrence of glucose < 50 mg/dL by continuous glucose monitoring.
8. Evaluate the safety and tolerability of CSI-Glucagon™ administered from an OmniPod® pump by assessing the following endpoints:
 - Incidence of adverse events (AEs) and serious adverse events (SAEs)
 - Laboratory safety variables
 - Physical examination
 - Vital signs

- Local tolerability: Erythema and/or edema formation at site of infusion assessed using the Draize scale

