7. STUDY DESIGN

7.1. Study Overview

This will be a Phase 2, multi-center, randomized, placebo-controlled, double-blind parallel group study with open-label follow-up designed to evaluate the efficacy of CSI-Glucagon™ for the prevention of hypoglycemia with lower IV glucose infusion rates when delivered subcutaneously to patients up to 1 year of age with congenital hyperinsulinism, using an OmniPod® infusion pump. CSI-Glucagon™ is expected to provide a better inpatient treatment option compared to the current standard of care.

The study will consist of three phases:

1. Baseline Phase: First is a baseline stabilization phase during which concomitant therapy with glucagon, octreotide and diazoxide will be safely weaned and continuous “basal” enteric feed will be held constant to the degree possible, with the only factors varying being meal size and IV GIR adjusted by a set plasma glucose measurement driven algorithm that stays unchanged throughout the end of period 3 and, thus, applies equally to both treatment groups. Basal enteric feeding will be held constant to the degree possible until the third phase of the study, except for extending the fast after meal feeding when the GIR is tapered off.
2. Blinded, Randomized Treatment Phase: Following the stabilization phase, subjects will be randomly assigned to blinded treatment with either glucagon or placebo, which will be delivered for up to 2 days with an OmniPod® pump with the controller set to a starting basal rate of 5 µg/kg/hr and GIR adjustments used to maintain euglycemia. After 48 hours of blinded treatment, all subjects will transition to open-label treatment in period 3.
 - a. At 24 hours, if GIR reduction from baseline is < 20%, subjects will be transitioned early to open-label drug.
3. Open-label Treatment Phase: The third study period will involve an initial assessment of the safety of a pump switch out, followed by use of CSI-Glucagon™ to manage glucose with minimal glucose infusions for a maximum of 28 days of cumulative exposure until a long-term management plan is in place. All subjects, even those meeting the criteria for treatment failure during phase 2, whether they received placebo or CSI-Glucagon™, will be eligible for the open-label treatment phase as long as such treatment is deemed to be beneficial in the judgement of the attending investigator.

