 - b. If GIR cannot be reduced because glucose level is < 70 mg/dL (3.9 mmol/L), **restore continuous enteric feeding if that has been suspended**, or increase glucose infusion rate by 2 mg/kg/min and **increase study drug infusion rate by 5 µg/kg/hour (to a maximum of 20 µg/kg/hr)** and check blood glucose in 1 hour.
 10. If glucose is <50 mg/dL (2.8 mmol/L), give 200 mg/kg dextrose by IV push, increase GIR by 2 mg/kg/min, **increase study drug infusion rate by 5 µg/kg/hour (to a maximum of 20 µg/kg/hr)** and check blood glucose in 30 minutes. At 12 hours after start of study drug, determine average GIR since the start of blinded therapy, excluding the first 2 hours. If average “on treatment” GIR has been reduced by < 20% from the baseline value determined in Period 1, take the following actions:
 - a. Remove the pump and weigh it.
 - b. Replace the pump with a new one at the same flow rate setting as the previous pump and a fresh supply of the same blinded study drug.
 - c. Monitor POC glucose over the next 12 hours, adjusting GIR using the same rules as above for making IV fluid adjustments in the interim.

{Note: This same procedure should be followed if the pump alarms or if there is an acute deterioration in an otherwise stable subject, indicating a possible occlusion.}

Day 1

At 24 hours after the initial start of study drug, determine average GIR since the start of blinded therapy, excluding the first 2 hours. Then compare the “on treatment” GIR to the baseline value determined in Period 1 and calculate the percentage change. Depending on percentage change in GIR, follow the procedures under either item 1 or item 2.

1. At 24 hours if average GIR has been reduced by < 20% from the baseline value determined in Period 1, complete the following procedures:

- a. Draw blood for plasma insulin and glucagon levels as well as CBC and CMP.
 - b. Remove and weigh the OmniPod® pump (Appendix 2) and:
 - a. Photograph the application site, paying particular attention to the cannula insertion site.
 - o Assess site for edema and erythema using the Draize scale. Any Draize scores >0 should be followed to resolution, including a follow-up photograph.
 - c. Proceed to Period 3 (see 10.2.3).
2. At 24 hours if average GIR has been reduced by $\geq 20\%$ from the baseline value determined in Period 1, complete the following procedures:
- a. Continue to adjust the GIR during day 1 as per day 0.

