12.3. Definition of an Adverse Event

An AE is any untoward medical occurrence in a clinical investigation subject administered a pharmaceutical product and which is not necessarily required to have a causal relationship with this treatment. An AE can therefore be any unfavorable and unintended sign, symptom, or disease temporally associated with the use of a medicinal product, whether or not considered related to the medicinal product. Examples of AEs include:

- Abnormal test findings
- Clinically significant symptoms and signs
- Changes in physical examination findings which are untoward and deemed clinically significant by the investigator.
- Allergy/hypersensitivity

The criteria for determining whether an abnormal objective test finding may be reported as an AE are as follows:

- Test result is associated with accompanying symptoms,
- Test result requires additional diagnostic testing or medical/surgical intervention,
- Test result leads to a change in study dosing or discontinuation from the study, significant additional concomitant drug treatment or other treatment, and/or
- Test result is considered to be an AE by the investigator or Sponsor.

Repeat of a test based on an abnormal result in the absence of the above conditions does not constitute an AE. Any abnormal test result determined to be an error does not require reporting as an AE.

A treatment-emergent AE (TEAE) is an AE that either commenced following initiation of study treatment or was present prior to study treatment but increased in frequency or severity following initiation of study treatment.

Standard medical terminology should be used in describing AEs. Informal descriptions should be avoided.

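### The Period 2 adverse-event comparison takes no account of blinded observation time, which the 24-hour response rule can make shorter on placebo if glucagon works

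*Combined protocol and SAP*

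**What the plan says.** Four statements bear on this point.

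- Section 13.2.5 sets the unit of safety analysis: "Safety/tolerability endpoints to be analyzed by treatment period will include" adverse events, laboratory variables, physical examination, body weight, vital signs and local tolerability.
- Section 13.2.5.1 specifies coding and a count: "A summary table indicating the number and the percentage of exposed subjects having at least one AE will be made".
- The Synopsis (Bio-statistical Considerations) supplies the test: "The proportion of study participants experiencing a particular AE will be compared by group (dose) using" Fisher's exact test.
- Section 7.1 sets the length of the blinded period: "At 24 hours, if GIR reduction from baseline is < 20%, subjects will be transitioned early to open-label drug". The Synopsis note on Period 3 gives the other branch: "For subjects meeting the criteria for response at 24 hours, the open-label period will begin after 48 hours of blinded study drug". Sections 10.2.2 and 10.2.3 repeat both branches.

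The plan gives no exposure-adjusted AE rate, no common cut-off time and no time-to-event method for AEs.

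**The concern.** Length of blinded observation is decided by response, and response is what the drug is meant to change. A percentage of infants with at least one event rises with time observed. If glucagon works, more active than placebo infants stay blinded for the second day, so more of them will have an AE for that reason alone. The distortion is absent if the drug does nothing and grows as it works better.

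The consequence is an AE contrast from the blinded period that can make a drug with no effect on an event look worse than placebo, or hide part of a true reduction. Other ways of reading the AE plan do not avoid the problem. Pooled over all periods, both arms may be on open-label glucagon after 24 or 48 hours. Tabulated by study drug, at most 48 hours of placebo stands against up to 28 days of glucagon.

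**Working it through.** **Inputs from the documents.** Planning failure rates are 0.9 on placebo and 0.1 on glucagon (section 13.1). Failure is less than 20% GIR reduction at 24 hours or less than 33% at 48 hours (section 5.1); only the first part shortens Period 2. Sample size is 6 per arm at the interim and 9 or 12 per arm at the end.

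**The plan's own figures.** Exact enumeration of the two-stage design gives early-stopping power of 65.9% at 0.9/0.1 (stated 66%) and 88.2% at 0.95/0.05 (stated 88%), and overall power of 99.0% at 0.9/0.1 (stated over 98%). The failure rates are therefore being read as the plan uses them.

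**Assumptions.** The share *s* of failures declared at 24 hours is not given; 1, 0.5 and 0 are shown. AE rates are not given; a constant rate *L* per infant-day, unrelated to response, is assumed.

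**Formulas.** With failure rate *f*, the probability of leaving at 24 hours is p24 = f × s.

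- Mean blinded hours = 24 × p24 + 48 × (1 − p24).
- P(any AE in Period 2) = p24 × (1 − e^(−L)) + (1 − p24) × (1 − e^(−2L)).

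**Example, s = 1, L = 0.5 in both arms.** 1 − e^(−0.5) = 0.3935 and 1 − e^(−1) = 0.6321.

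- Hours: placebo 24 × 0.9 + 48 × 0.1 = 26.4; glucagon 24 × 0.1 + 48 × 0.9 = 45.6.
- AE proportion: placebo 0.9 × 0.3935 + 0.1 × 0.6321 = 0.417; glucagon 0.1 × 0.3935 + 0.9 × 0.6321 = 0.608.
- Risk ratio: 0.608 / 0.417 = 1.46.

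**Results with 0.5 per infant-day on placebo.** The halved rate on glucagon is 0.25.

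| Window | Hours, placebo / glucagon | Equal rates: placebo / glucagon | RR | True halving: placebo / glucagon | RR |
|---|---|---|---|---|---|
| Period 2, s = 1 | 26.4 / 45.6 | 41.7% / 60.8% | 1.46 | 41.7% / 37.6% | 0.90 |
| Period 2, s = 0.5 | 37.2 / 46.8 | 52.5% / 62.0% | 1.18 | 52.5% / 38.5% | 0.73 |
| Period 2, s = 0 | 48 / 48 | 63.2% / 63.2% | 1.00 | 63.2% / 39.3% | 0.62 |
| First 24 h | 24 / 24 | 39.3% / 39.3% | 1.00 | 39.3% / 22.1% | 0.56 |

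The gap between 0.62 and 0.56 is not bias. It arises because a proportion saturates over a longer window.

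**Range over the rate, s = 1, equal rates.** At 0.1 per day, 10.4% against 17.3% (RR 1.66). At 1.0 per day, 65.5% against 84.1% (RR 1.28).

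**Behaviour of the test, s = 1, equal rates of 0.5 per day.** Two-sided testing at 0.05 is assumed, because the plan does not state sidedness for AEs. Fisher's test rejects in 1.9% of trials at 6 per arm, 6.4% at 9 and 9.0% at 12. At 12 per arm a common 24-hour window would give 2.1%. More glucagon than placebo infants have the event in 65% of trials at 6 per arm (the reverse in 17%) and in 77% at 12 per arm (the reverse in 12%). With a common 24-hour window at 12 per arm it is 42% each way.

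**How often each size occurs at 0.9/0.1.** The interim rule stops at 6 per arm in 66% of trials, goes to 9 in 23% and to 12 in 11%. Weighting the rejection rates gives 0.66 × 1.9 + 0.23 × 6.4 + 0.11 × 9.0 = 3.7%. This ignores the dependence between stopping and exposure.

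**The case against.** The strongest reply is that the size of the problem is unknown and may be small. Only the 24-hour part of the composite shortens Period 2. The 0.9 and 0.1 rates are power scenarios for the whole composite, and baseline GIR is an average over the weaning procedure, so some placebo infants may pass the 24-hour rule without drug. A reader might infer that Period 2 is about half as long on placebo; that is the limiting case, not something the documents establish. This objection stands.

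A reader might also expect many false-positive safety signals. At these planning rates the trial usually stops at 6 per arm, where the test seldom rejects, and the size-weighted rate is below 5%. For an uncommon AE the distortion is slight in absolute terms: at 0.1 per day and 6 per arm, even with every failure at 24 hours, the expected excess is 6 × (0.173 − 0.104) = 0.4 infants.

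A third tempting reading is that this comparison chiefly misjudges hypoglycemia. Low glucose is not named as an AE. It can enter through the section 12.3 criteria for abnormal tests, such as "Test result leads to a change in study dosing or discontinuation from the study", and glucose below 50 mg/dL does trigger an order to "give 200 mg/kg dextrose by IV push, increase GIR by 2 mg/kg/min" and to raise study drug. But section 12.3 says only that such findings may be reported. The planned glucose comparison, "Compare proportional time < 70 mg/dL as well as proportional time in euglycemia" (section 5.2, item 5), is already normalised for time. Its lack of a method in section 13 is a separate gap.

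Finally, the test by period comes from joining the Synopsis to section 13.2.5; the Synopsis sentence mentions group, not period, and section 13.2.5.1 is descriptive. That is fair, but the percentages by period carry the same bias with or without a test. Nor do the two rules contradict each other, since both can be carried out. The difficulty is what their combination estimates.

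**Conclusion.** The point holds as a bias in estimation. As written, the Period 2 AE percentages compare arms over blinded times that depend on response, and they are biased against an effective drug. Under an equal assumed rate of 0.5 per infant-day and the 0.9/0.1 planning rates, the apparent risk ratio is 1.46, 1.18 or 1.00 when all, half or none of the failures are declared at 24 hours. A true halving appears as 0.90, 0.73 or 0.62.

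These figures rest on the assumed share and on a constant AE rate unrelated to response. Events concentrated in the first hours would be distorted less.

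It would be too strong to call the AE table the trial's only placebo-controlled safety result: laboratory variables, vital signs and local tolerability are also analysed by period. The primary analysis is not touched. Severity is minor to moderate.

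**What to change.** In section 13.2.5.1, make the between-arm AE comparison over the first 24 blinded hours, common to both arms, for all treated infants by randomised arm. Report the whole of Period 2, including hours 24 to 48, with infant-hours of exposure and events per infant-day by arm, in place of Fisher's test on raw proportions. Describe Period 3 separately. Align the Synopsis sentence with this.

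The cost is a change of wording and one AE table by time window. It needs AE onset times, which assigning events to a treatment period already requires.

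The downside is that the formal comparison omits the second blinded day. It will see fewer events, and precision at 6 to 12 infants per arm stays low. Later-onset events, such as infusion-site reactions, would be described rather than tested. Hours 24 to 48 should in any case be read as descriptive, because only infants who met the 24-hour criterion remain blinded then.

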13.2.5.5. Local Tolerability

The incidences of erythema and edema will be analyzed with a McNemar's test.

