9. STUDY TREATMENTS

9.1. Allocation to Treatment

Subjects will be enrolled until 12 evaluable patients fulfilling all final protocol GIR selection criteria complete period 2 of the study across all investigational sites, at which point an interim analysis will be conducted. The randomization will be adaptive with a minimization procedure to balance glucose infusion rate at baseline and non-evaluable patients and subjects not fulfilling all final protocol GIR selection criteria will be replaced. The final sample size is tentatively projected at 24, but may adapt based on the planned interim analysis (see Section 13.4).

Each subject will receive a basal subcutaneous infusion from an OmniPod® infusion pump placed on the anterior abdomen, 5-10 cm away from the umbilicus as per manufacturer's directions. Based on the prior experience of the investigators in treating CH patients with glucagon, the starting basal infusion rate for the subjects will be set at 5 µg/kg/hr, but this can be adjusted as necessary for a particular subject based on the GIR determined in period 1.

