9.3. Drug Supplies

9.3.1. Drug Product Formulation and Packaging

CSI-Glucagon™ is a room temperature stable, non-aqueous, injectable liquid formulation of glucagon. The formulation consists of 5 mg/mL synthetic glucagon peptide dissolved in a primary DMSO solvent, with trehalose added as stabilizing excipients. A volume of 1 mL of formulation is filled into West Pharmaceutical's 2 mL Crystal Zenith® pre-filled cyclic olefin polymer (plastic) vial with Flurotec® coated stopper. The drug product is stored at controlled room temperature (20-25°C) prior to use.

The placebo comparator to be used in this study is the vehicle for CSI-Glucagon™. It contains no glucagon, but otherwise has the same composition and is indistinguishable in appearance from the test product.

The CSI-Glucagon™ and matching placebo are packaged, labeled and distributed for Xeris under cGMP by MRI Global (Kansas City, MO).

For use during blinded Period 2, sites will be provided with a supply of active and placebo product packaged in identical vials with the same blinded label on each. A separate set of unblinded vials of active product will be supplied for use during open-label Period 3.

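### Section 13.2.5.5 names a paired test for erythema and edema but no pairs, unit or cut-off, and leaves Draize scores that are not adverse events without a valid comparison between the randomized arms

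*Combined protocol and SAP*

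**What the plan says.** Local tolerability is a listed endpoint under secondary objective 8 in Section 5.2: "Local tolerability: Erythema and/or edema formation at site of infusion assessed using the Draize scale". Its analysis is Section 13.2.5.5, in full: "The incidences of erythema and edema will be analyzed with a McNemar's test". The lead-in to Section 13.2.5 reads "Safety/tolerability endpoints to be analyzed by treatment period will include", followed by a list that includes local tolerability.

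Section 7.1 describes a "randomized, placebo-controlled, double-blind parallel group study with open-label follow-up". Section 9.3.1 states "The placebo comparator to be used in this study is the vehicle for CSI-Glucagon".

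Two general statements in the synopsis also bear on the point. One is "Safety data will be presented in tabular and/or graphical format and summarized descriptively". The other is "The proportion of study participants experiencing a particular AE will be compared by group (dose) using" Fisher's exact test. Under Section 13.2.5.3 a change on physical examination becomes an adverse event only when the investigator considers it clinically significant.

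Section 10.2.2 calls for a photograph of the site before the pump is applied. Appendix 1 places the Draize examination after the pump is removed. A score above 0 appears only as a trigger for follow-up, not as an analysis cut-off.

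**The concern.** McNemar's test compares two binary results on the same unit and uses only the discordant pairs. The plan does not say which two results are meant, so two statisticians could run different tests and both comply. The reading that matters most, glucagon against vehicle in Period 2, is not a paired comparison at all.

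Period 2 is the only randomized comparison of infusion-site reactions in the trial. Because placebo is the vehicle, that comparison isolates what glucagon adds to the local effect of solvent and pump. If the contrast, unit and cut-off are still open at unblinding, the choice becomes post hoc. If the paired test is run as written, its p-value may be read as a statement about glucagon against vehicle when it is not a comparison of the randomized arms.

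**Working it through.** **Step 1. Which pairs could the sentence mean?**

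| Candidate contrast | Paired? | What it would show |
|---|---|---|
| Glucagon vs vehicle, Period 2 | No: different infants (7.1) | McNemar does not apply |
| Before vs after wear | No: photograph only beforehand (10.2.2); Draize after removal (Appendix 1) | No score to pair with |
| Period 2 vs Period 3, placebo arm | Yes | Vehicle then glucagon, fixed order, unequal wear |
| Period 2 vs Period 3, active arm | Yes | Glucagon then glucagon |
| Other within-infant pairs (two pumps in one period; erythema vs edema at one site) | Yes | Not glucagon against vehicle |

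Wear differs by design. A Period 2 site is worn 24 or 48 h, or 12 h followed by 12 or 36 h after the 12-hour pump change in 10.2.2; alarms or deterioration can add changes. In Period 3 the first pump is worn 4 h and later ones up to 72 h (10.2.3).

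**Step 2. Power, under assumptions.** The documents give no reaction rates and no power for this endpoint. Assumed: vehicle 1/6 (17%), glucagon 2/3 (67%), one site per period, equal wear, two-sided 5%. The plan supplies 6, 9 and 12 per arm; 15 is added because under Section 9.1 "non-evaluable patients and subjects not fulfilling all final protocol GIR selection criteria will be replaced", so the Safety cohort may exceed 12.

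- Fisher, between arms in Period 2: sum of Bin(i; n, 2/3) × Bin(j; n, 1/6) over tables with p ≤ 0.05.
- Exact McNemar: binomial test on the discordant pairs. Six pairs all one way give 2 × 0.5^6 = 0.031; five give 0.0625.
- Independent periods: placebo-arm discordance is 1/6 × 1/3 = 0.056 one way and 5/6 × 2/3 = 0.556 the other; active-arm discordance is 2/3 × 1/3 = 0.222 each way.
- Maximal positive within-infant correlation: placebo-arm discordance is 0 and 2/3 − 1/6 = 0.5; active-arm discordance is 0. Power is then P(Bin(n, 0.5) ≥ 6).

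| Test | 6 | 9 | 12 | 15 per arm |
|---|---|---|---|---|
| Fisher, Period 2 | 15% | 45% | 61% | 69% |
| McNemar, arms pooled, independent | 8% | 18% | 28% | 38% |
| McNemar, arms pooled, maximal correlation | 2% | 25% | 61% | 85% |
| McNemar, placebo arm only, independent | 3% | 28% | 51% | 68% |

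**Step 3. Assumed worst case if the unit is left open.** Take 24 pairs, no drug effect, independent sites, per-site risk r of 5% to 20%, and an any-site endpoint, so an infant with k sites reacts with probability 1 − (1 − r)^k. McNemar rejects in at most 1.8% with one site per period, at most 2.4% with 2 vs 2, 0.9% to 14% with 1 vs 2, and 77% to 99.9% at the extreme of 1 vs 10. The excess comes from unequal site counts, not from McNemar's test itself.

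**Step 4. Limits of the replacement.** Take no drug effect, 12 per arm, the plan's failure rates of 0.9 and 0.1, and a reaction risk of 20% to 70% (per 48 h or per insertion).

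- First site, risk per insertion: Fisher rejects in at most 2.3%.
- First site, risk per hour, every failure having the 12-hour change: mean wear is 0.9 × 12 + 0.1 × 48 = 15.6 h on placebo and 0.1 × 12 + 0.9 × 48 = 44.4 h on active. Fisher rejects in 2.4% to 29.7%, against active. If half of the failures keep the first pump to 48 h, this falls to 1.4% to 7.6%.
- Any site, risk per hour, failures ending at 24 h: 1.6% to 9.4%, against active.
- Any site, risk per insertion: mean insertions are 0.9 × 2 + 0.1 × 1 = 1.9 on placebo and 0.1 × 2 + 0.9 × 1 = 1.1 on active; 4.4% to 9.3%, against placebo.

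**The case against.** The strongest reply is that little is left uncovered. Safety data are to be summarized descriptively, clinically significant reactions become adverse events, and those get a between-group Fisher test. What remains is lesser Draize scores in 6 to 12 infants per arm, for which a p-value has low power. That stands as a limit on importance. It does not supply the missing definition, and it does not make the one test the plan names for this endpoint fit the randomized comparison.

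A reader might infer more than the documents support, in three ways.

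- *That McNemar's test can say nothing about glucagon against vehicle.* Placebo-arm infants receive vehicle and later open-label glucagon, so a within-infant contrast can be computed. It is confounded by order and wear, and the plan does not name it, but it exists.
- *That McNemar's test dilutes the effect or is weaker than Fisher's.* This depends on the within-infant correlation. At 12 per arm the pooled test runs from 28% to 61%, against 61% for Fisher; at 15 per arm and maximal correlation it is ahead, 85% to 69%.
- *That the plan intends a pooled, any-site test of Period 2 against Period 3.* The Section 13.2.5 lead-in may mean only separate summaries for each period. Step 3 shows what an undefined endpoint permits, not what is planned.

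**Conclusion.** The point holds for the randomized comparison. The plan assigns a paired test to an endpoint whose only randomized contrast is unpaired, and defines neither pairs, unit nor cut-off. This rests on the text alone and needs no assumed rate. The argument is about interpretability, not about which test has more power.

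Every figure in Steps 2 to 4 depends on assumed reaction rates, and Steps 3 and 4 include deliberate extremes. The consequence is confined to one safety endpoint in a small Phase 2 trial. The change should be made, before unblinding, but it is not critical.

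**What to change.** Replace the sentence in Section 13.2.5.5 with:

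> In the Safety cohort, the number and proportion of infants with Draize erythema >0, and separately edema >0, in Period 2 will be reported by arm, with an exact confidence interval for the difference and an exploratory Fisher's exact test. The first Period 2 site is the main per-infant result; any Period 2 site is supporting. Wear time and number of insertions will be reported by arm. Period 3 reactions will be summarized descriptively. McNemar's test will be used only for an explicitly defined within-infant contrast with one pre-specified site per period.

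Add a cross-reference to Appendix 1 at the 12-hour pump change in Section 10.2.2 and in Table 4. Appendix 1 already requires the site to be examined after removal, but the steps for that change do not mention it, and Table 4 lists Draize scoring on Day 1, Day 2 and Q3D, not on Day 0 when the change falls.

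The cost is one paragraph and the cross-reference, with no new visits, samples or assessments. The drawback is that the comparison stays exploratory and low in power, and unequal wear or number of insertions can bias it in either direction, so its p-value should not be read without the wear data.
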